5 STUDY PROCEDURES AND ASSESSMENTS

5.1 Visits and Examinations

5.1.1 Visit 1 (Day 1) – Baseline/Dispense Lens 1

1	Explain the purpose and nature of the study, and have the subject read, sign, and date the IRB-approved informed consent document. Additionally, have the individual obtaining consent from the subject and a witness, if applicable, sign and date the informed consent document. Provide a photocopy of the signed document to the subject and place the original signed document in the subject's chart. After signing the ICF, a subject will be assigned a subject number by the EDC system. A signed informed consent document defines the point of enrollment.
2	Obtain demographic information and medical history, including information on all medications used within the past 30 days. Include herbal therapies, vitamins, and all over-the-counter as well as prescription medications.

3	
4	
Perform Snellen VA with habitual correction.
 
 • OD, OS, distance only, contact lenses • Over-refraction (only needed if VA is reduced) 
Record habitual lens information (brand, power).

5	
6	
7	
Perform slit-lamp biomicroscopy (without contact lenses) to evaluate the following:
 
 • Limbal hyperemia • Bulbar hyperemia • Corneal staining • Conjunctival staining • Palpebral conjunctival observations • Corneal epithelial edema • Corneal stromal edema • Corneal vascularization • Conjunctival compression/indentation • Chemosis • Corneal infiltrates • Other findings
8	
Determine study lens powers based upon the manifest refraction and habitual lens powers.

9	
Review inclusion/exclusion criteria to determine if the subject qualifies to be randomized into the study. If subject qualifies, request randomization. If subject does not qualify, exit the subject from the study as a screen failure.

10	
Based upon the randomized treatment sequence assignment, have the subject insert the appropriate study lenses.
 
 • Keep all lidding foils of lenses used during lens fit process for study lens accountability. • Follow procedures to maintain masking.
11	
[REDACTED]
 
[REDACTED]
 
[REDACTED]

12	
Evaluate the study lenses by performing the following:
 
 • Snellen VA with study lenses (OD and OS, at distance)* • Over-refraction if necessary to determine the best contact lens-corrected VA and final study lens power(s) 
*VA w/study lenses must be 20/40 OU or better for subject to leave the office

13	
[REDACTED]

14	
Assess and record any AEs and device deficiencies reported or observed during the study visit.
 
Note: AEs and device deficiencies must be recorded for all enrolled subjects (including those that screen fail) from the time of signature of informed consent.

15	
Dispense study lenses (Lens 1). Provide the subject with written and verbal instructions on lens wear.

16	
Schedule Visit 2 to take place on Day 8 (-1/+2 days) of lens wear (Lens 1).

17	
Note: If for some reason a subject is unable to wear a study lens for the duration of this visit window, instruct the subject to return to the site for an Unscheduled Visit as well as lens removal on site, if possible. The subject should then be scheduled to return to the clinic for Visit 2 (if possible) or exited from the study.

5.1.2 Visit 2, Week 1 [Day 8 (-1/+2 Days)] – Follow-up Lens 1/Dispense Lens 2

1	Obtain information on any changes in medical health and/or the use of concomitant medications.
2	Record any device deficiencies or AEs including those associated with changes in concomitant medication dosing, which are observed or reported since the previous visit(s).
3	Review subject compliance with lens wear and adjunct product usage.
4	Administer Subjective Questionnaire to assess the following: 
• [REDACTED]• [REDACTED]• [REDACTED]• [REDACTED]• Subjective overall quality of vision, OU• [REDACTED]• [REDACTED]
5	Evaluate the study lenses by performing the following: 
• Snellen VA with study lenses (OD and OS, at distance)
6	[REDACTED]

7	
Perform slit-lamp biomicroscopy (without contact lenses) to evaluate the following:
 
• Limbal hyperemia• Bulbar hyperemia• Corneal staining• Conjunctival staining• Palpebral conjunctival observations• Corneal epithelial edema• Corneal stromal edema• Corneal vascularization• Conjunctival compression/indentation• Chemosis• Corneal infiltrates• Other findings
8	
Based upon the randomized treatment sequence assignment, have the subject insert the Lens 2 study lenses to be evaluated.
 
Note: Keep all lidding foils of lenses used during lens fit process for study lens accountability.

9	
[REDACTED]

10	
Evaluate the study lenses by performing the following:
 
• Snellen VA with study lenses (OD and OS, at distance)*• Over-refraction if necessary to determine the best contact lens-corrected VA and final study lens power(s) 
*VA w/study lenses must be 20/40 OU or better for subject to leave the office

11	
[REDACTED]

12	
Assess and record any AEs and device deficiencies reported or observed during the study visit.
 
Note: AEs and device deficiencies must be recorded for all enrolled subjects from the time of signature of informed consent regardless of their enrollment status (screen failure or randomized).

13	Dispense study lenses (Lens 2). Provide the subject with written and verbal instructions on lens wear.
14	Schedule Visit 3 to take place on Day 8 (-1/+2 days) of lens wear (Lens 2).
15	Note: If for some reason a subject is unable to wear a study lens for the duration of this visit window, instruct the subject to return to the site for an Unscheduled Visit as well as lens removal on site, if possible. The subject should then be scheduled to return to the clinic for Visit 3 (if possible) or exited from the study.

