1 PROTOCOL SYNOPSIS

Trial Sponsor	Alcon Research, Ltd. [name]
Name of Test Product	DD T2
Name of Control Product	CooperVision® clariti® 1 day (Clariti 1 Day)
Title of Trial	Clinical Comparison of Two Daily Disposable Soft Contact Lenses
Protocol Number	CLE383-C006
Number of Sites	~1
Country	US
Planned Duration of Exposure	~20 days total duration 
 • Test Product: 8 days (-1/+2 days) • Control Products: 8 days (-1/+2 days)
Number of Subjects	Target to complete: 20
	Planned to enroll: ~22
Study Population	Volunteer subjects aged 18 or over who are soft daily disposable contact lens wearers (excluding current Clariti 1 Day wearers), have at least 3 months of contact lens wearing experience, and who wear their habitual lenses at least 5 days per week and at least 8 hours per day.
Objectives	The primary objective of this study is to evaluate the overall performance of DD T2 lenses when compared to Clariti 1 Day lenses.
Endpoints	Primary Effectiveness 
 • Overall quality of vision
	 
Safety
 
 • AEs • Biomicroscopy findings • Device deficiencies

Assessments
	
Effectiveness
 
 - VA (Snellen distance) 

 
 - Overall quality of vision 

 
Safety
 
 - AEs - Biomicroscopy - Device deficiencies 	

Study Design
	
 Prospective
 
 Single group
 
 Parallel group
 
 Crossover
 
 Other
 
 Contralateral
 
 Bilateral
 
 Monocular lens wear
	
 Single-masked (trial subject)
 
 Single-masked (Investigator)
 
 Double-masked
 
 Open-label
 
 Other
 
 Randomized

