
This is a randomized, prospective crossover study design. Approximately 22 subjects will be randomized to 1 of the 2 lens sequences consisting of 2 crossover sequences of test vs. control. Subjects will wear the assigned study Lens 1 bilaterally for approximately 1 week before crossing over into the assigned study Lens 2 bilaterally for approximately 1 week.
 
Study Visits:
 
 1. Baseline/Dispense Lens 1 2. Day 8 (-1/+2 days) follow-up Lens 1/Dispense Lens 2 3. Day 8 (-1/+2 days) follow-up Lens 2/Exit 		

Test Product Details
	
Primary component/material
	

Product Name
		
DD T2

	LID Number	LID006841
	Manufacturer	Alcon
	Other	The lenses will be available in -1.75 D to -4.50 D (0.25 D steps)
Control Product Details	Primary component/material	somofilcon A
	Product Name	Clariti 1 Day
	LID Number	LID014044
	Manufacturer	CooperVision
	Other	The lenses will be available in -1.75 D to -4.50 D (0.25 D steps)
Inclusion Criteria	
 1. Subject must be at least 18 years of age. 2. Subject must be able to understand and must sign an ICF that has been approved by an IRB. 3. Successful wear of daily disposable spherical soft contact lenses in both eyes for a minimum of 5 days per week and 8 hours per day during the past 3 months. 4. Manifest cylinder ≤ 0.75 D in each eye. 5. BCVA 20/25 or better in each eye. 6. Subject must be willing to stop wearing their habitual contact lenses for the duration of study participation. 	

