3.4 Subject Population

The study population includes approximately 22 volunteer subjects to be enrolled at approximately 1 site. The study population will consist of subjects with normal eyes (other than the need for optical correction for myopia), and who are adapted, existing wearers of daily disposable soft contact lenses in both eyes.

Subjects must be screened according to the full list of inclusion/exclusion criteria in Section 1 of this protocol. Rescreening of subjects is not allowed in this study.

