5.3 Discontinued Subjects

Discontinued subjects are those who withdraw or are withdrawn from the study after signing the informed consent, including screen failures. Subjects may discontinue from the study at any time for any reason. Subjects may also be discontinued from the study at any time if, in the opinion of the Investigator, their continued participation poses a risk to their health. Discontinued subjects will not be replaced (ie, their subject numbers will not be re-assigned/re-used).

Should a subject exhibit any clinically relevant signs, symptoms, or other clinical observations that possibly could be associated with suspected sensitivity or intolerance to one of the study treatments, the Investigator must document those observations on an AE Form.

Any subject who exits early from the study (excluding screen failures) must undergo all procedures outlined at Visit 3, as applicable.

The Investigator must document the reason for study or treatment discontinuation in the subject's case history source documents.

To ensure the safety of all subjects who discontinue early, Investigators must assess each subject and, if necessary, advise them of any therapies and/or medical procedures that may be needed to maintain their health.

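### Does giving about 22 as both the number enrolled and the number randomised put the 20 completers at risk?

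*Protocol*

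**What the plan says.** Three counts appear in the plan.

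- **Enrolled.** The Protocol Synopsis gives "Planned to enroll: ~22". Protocol Section 3.4 repeats the figure ("approximately 22 volunteer subjects to be enrolled at approximately 1 site"), and so does SAP Table 1-1.
- **Randomised.** The study design text in the Synopsis says "Approximately 22 subjects will be randomized to 1 of the 2 lens sequences". SAP Section 1.3 adds that only qualifying subjects are randomised, 1:1.
- **Completing.** The Synopsis gives "Target to complete: 20".

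Protocol Section 5.1.1 puts enrolment at step 1: "A signed informed consent document defines the point of enrollment". Biomicroscopy is step 7 and the eligibility review is step 9, where the instruction is: "If subject does not qualify, exit the subject from the study as a screen failure". The adverse event note at step 14 treats screen failures as enrolled. Section 5.3 also counts them as discontinued: "Discontinued subjects are those who withdraw or are withdrawn from the study after signing the informed consent, including screen failures". It says that discontinued subjects are not replaced, and explains in the same sentence that this means their subject numbers are not reissued. Section 3.4 rules out rescreening.

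**The concern.** Enrolled and randomised are different populations under the protocol's own definitions, but they carry the same figure. Anyone who consents and then fails the eligibility review uses up a place among the enrolled without being randomised. A site that counted consents and stopped at 22 would randomise fewer than 22, and the margin of 2 between 22 and 20 would have to absorb both screen failure and dropout.

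Screen failure is possible here. There are 15 exclusion criteria, limits on cylinder and corrected acuity, and lenses only from -1.75 to -4.50 D, with study lens power settled after consent. Read without its explanation, the no-replacement sentence in Section 5.3 seems to close off any remedy. What would be at stake is a small crossover study, about 11 per sequence, that ends short of its stated number of completers.

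**Working it through.** **Inputs.** Completers: 20 (Synopsis). Enrolled: about 22 (Synopsis, Section 3.4, SAP Table 1-1). Randomised: about 22 (Synopsis, study design). The visible text gives no screen-failure rate *s* or dropout rate *d*, so both are assumed below and shown as a range.

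**1. Where 22 could come from.** It cannot be derived from the documents, but it can be checked for plausibility as 20 inflated for dropout, 20 / (1 − d) rounded up:

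- d = 5%: 20 / 0.95 = 21.05, so 22
- d = 9.1%: 20 / 0.909 = 22.0, so 22
- d = 10%: 20 / 0.90 = 22.2, so 23

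A dropout allowance of 5% to 9.1%, with nothing for screen failure, gives exactly 22. The figure therefore behaves like a number randomised.

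**2. If 22 were a ceiling on consents.** The allowed loss is 22 − 20 = 2, and 2/22 = 9.1%. With p = (1 − s)(1 − d), expected completers are 22p, and the chance of at least 20 is the upper tail of a binomial(22, p):

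| s (assumed) | d (assumed) | Expected completers | P(at least 20) |
|---|---|---|---|
| 0% | 5% | 20.9 | 0.905 |
| 5% | 5% | 19.9 | 0.636 |
| 10% | 5% | 18.8 | 0.362 |
| 10% | 10% | 17.8 | 0.183 |
| 20% | 5% | 16.7 | 0.074 |

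The result depends almost wholly on rates that have to be assumed.

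**3. If 22 is the number randomised.** Consents needed are 22 / (1 − s), rounded up: 24 at 5% screen failure (22 / 0.95 = 23.2), 25 at 10% (24.4) and 28 at 20% (27.5). Screen failure then drops out of the calculation. The chance of at least 20 completers is 0.905 at 5% dropout and 0.620 at 10%.

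**4. Which reading the text supports.** The consent definition says when a person counts as enrolled; it does not say when recruitment stops. Every 22 is qualified as approximate. The Synopsis separately states the number to be randomised. The explanation attached to the no-replacement sentence concerns reuse of subject numbers and does not clearly bar further recruitment. Reading 3 agrees with the explicit randomisation statement. Reading 2 needs a cap that no visible passage sets.

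**5. What a shortfall would cost.** SAP Section 4.3.1 plans a two-sided 95% confidence interval for the mean rating of each lens. Its half-width in SD units is t / √n:

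- n = 20: 2.093 / √20 = 0.468
- n = 19: 2.101 / √19 = 0.482
- n = 18: 2.110 / √18 = 0.497
- n = 17: 2.120 / √17 = 0.514

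With 18 subjects instead of 20 the interval is 0.497 / 0.468 = 1.06 times as wide. With 17, close to the worst row of the table, it is 0.514 / 0.468 = 1.10 times as wide.

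**The case for a change.** The best case for a change is that a site needs one unambiguous count at which to stop, and the protocol offers two. At 20% screen failure, 28 consents are needed to randomise 22, and it is hard to call 28 approximately 22. The repair would cost only wording, and the arithmetic in step 1 suggests that the number randomised was meant.

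Part of this stands. The double use of the figure is real, and separate numbers for consented, randomised and completing would read better. What does not stand is the step from loose wording to a likely shortfall. That needs a cap on consents, which the plan does not contain, and loss rates, which the visible text does not give. A heading after Protocol Section 6.9 is redacted in the contents list, so an allowance may be set out there, and its absence from the visible text cannot be held against the plan.

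The stake is also smaller than it looks. Both documents state that no inference is made on the primary endpoint, and the SAP says success criteria do not apply, so 20 is a target and no power calculation rests on it. The effectiveness set is everyone exposed to a study lens, so a subject who leaves after rating Lens 1 can still contribute that rating if evaluable. The visible primary analysis is by lens, not by sequence, so about 11 per sequence adds no weight. Relabelling would not guarantee 20 completers either: at 10% dropout the chance is 0.620 even with 22 randomised.

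**Conclusion.** No change to the plan is needed. The same approximate figure is used for two populations that match exactly only when nobody fails screening. This is a slip in terminology, and the explicit statement that about 22 will be randomised resolves it in practice. Enrolment and randomisation are separate recorded events in Section 5.1.1, so analysts can count consented, randomised and completing subjects without relying on the planning figure.

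The shortfall probabilities are correct for their assumed rates, but they apply only if approximately 22 is taken as a hard limit on consents. Even then, a loss of two subjects from 20 widens each per-lens 95% interval by about 6%, and a loss of three by about 10%, for the same SD. No test, success criterion or decision in the plan turns on a difference of that size. This conclusion rests on the visible text, and on the no-replacement sentence meaning what its own explanation says.

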5.1.3 Visit 3, Week 2 [Day 8 (-1/+2 Days)] – Follow-up Lens 2/Exit

1	Obtain information on any changes in medical health and/or the use of concomitant medications.
2	Record any device deficiencies or AEs including those associated with changes in concomitant medication dosing, which are observed or reported since the previous visit(s).
3	Review subject compliance with lens wear and adjunct product usage.
4	Administer Subjective Questionnaire to assess the following: 
 • [REDACTED] • [REDACTED] • [REDACTED] • [REDACTED] • Subjective overall quality of vision, OU • [REDACTED] • [REDACTED] • [REDACTED]
5	Evaluate the study lenses by performing the following: 
 • Snellen VA with study lenses (OD and OS, at distance)
6	[REDACTED]

7	
Perform slit-lamp biomicroscopy (without contact lenses) to evaluate the following:
 
 • Limbal hyperemia • Bulbar hyperemia • Corneal staining • Conjunctival staining • Palpebral conjunctival observations • Corneal epithelial edema • Corneal stromal edema • Corneal vascularization • Conjunctival compression/indentation • Chemosis • Corneal infiltrates • Other findings
8	
Assess and record any AEs and device deficiencies reported or observed during the study visit.
 
Note: AEs and device deficiencies must be recorded for all enrolled subjects from the time of signature of informed consent regardless of their enrollment status (screen failure or randomized).

9	
Perform Snellen VA with habitual correction.
 
 • OD, OS, distance only, contact lenses 
Note: If this VA with habitual correction shows a decrease of 2 lines or more versus Visit 1 baseline VA with habitual correction, then BCVA with MR is required to confirm a potential loss in VA for AE reporting requirements (see Section 7).

10	
Exit the subject from the study.

5.2 Unscheduled Visits

Any visit that occurs between regularly scheduled visits is an Unscheduled Visit. If a subject requires an Unscheduled Visit, he/she must be advised to return to the office wearing the study lenses, if at all possible (unless he/she is experiencing a sign or symptom [as indicated in Section 3.3 Risks and Benefits]). During all unscheduled visits, the Investigator must conduct the following procedures:

- Collect AE and device deficiency information
- Assess and record changes in medical condition or concomitant medication
- Assess and record VAs

- Perform biomicroscopy (assessments with or without lenses, as possible)

In addition, all procedures for Visit 3 (Follow-up Lens 2/Exit) should be completed (as possible). The Investigator may perform additional procedures for proper diagnosis and treatment of the subject. The Investigator must document this information in the subject's case history source documents.

If during an Unscheduled Visit the subject is discontinuing the study lenses or discontinuing from the study, the Investigator must conduct Exit procedures according to Table 1-1: Schedule of Study Procedures and Assessments, as possible.

5.3 Discontinued Subjects

Discontinued subjects are those who withdraw or are withdrawn from the study after signing the informed consent, including screen failures. Subjects may discontinue from the study at any time for any reason. Subjects may also be discontinued from the study at any time if, in the opinion of the Investigator, their continued participation poses a risk to their health. Discontinued subjects will not be replaced (ie, their subject numbers will not be re-assigned/re-used).

Should a subject exhibit any clinically relevant signs, symptoms, or other clinical observations that possibly could be associated with suspected sensitivity or intolerance to one of the study treatments, the Investigator must document those observations on an AE Form.

Any subject who exits early from the study (excluding screen failures) must undergo all procedures outlined at Visit 3, as applicable.

The Investigator must document the reason for study or treatment discontinuation in the subject's case history source documents.

To ensure the safety of all subjects who discontinue early, Investigators must assess each subject and, if necessary, advise them of any therapies and/or medical procedures that may be needed to maintain their health.

5.4 Clinical Study Termination

The Study Sponsor reserves the right to close the investigational site or terminate the study in its entirety at any time, for reasonable cause.

If the clinical study is prematurely terminated or suspended by the Study Sponsor:

- The Study Sponsor must:

- Immediately notify the Investigator(s) and subsequently provide instructions for study termination.
- Inform the Investigator and the regulatory authorities of the termination/suspension and the reason(s) for the termination/suspension, as applicable.
- The Investigator must:
 - Promptly notify the IRB of the termination or suspension and of the reasons.
 - Provide subjects with recommendations for post-study treatment options as needed.

The Investigator may terminate a site's participation in the study for reasonable cause.

6 ANALYSIS PLAN

Continuous variables will be summarized using the number of observations, mean, standard deviation, median, minimum, and maximum. Categorical variables will be summarized with counts and percentages from each category. Any deviations to this analysis plan will be updated during the course of the study as part of a protocol amendment or will be detailed in the clinical study report.

6.1 Subject Evaluability

The final subject evaluability will be determined prior to breaking the code for masked treatment sequence assignment and locking the database, based on the Deviations and Evaluability Plan.

6.2 Analysis Data Sets

6.2.1 Safety Analysis Set

Safety analyses will be conducted using the safety analysis set on a treatment-emergent basis. As such, the safety analysis set will include all subjects/eyes exposed to any study lenses evaluated in this study. For treatment-emergent safety analyses, subjects/eyes will be categorized under the actual study lens exposed in the corresponding lens sequence.

6.3 Demographic and Baseline Characteristics

Demographic information (age, sex, ethnicity, race) will be summarized on the Safety Analysis Set. Baseline data pertaining to habitual lens [REDACTED] [REDACTED] will be summarized on the Safety Analysis Set as well.

